6.4.4. Exploratory Analysis of Antibody-Mediated Immunogenicity Endpoints

- GMT of ZIKV-specific nAbs, in all participants, in initially flavivirus-seronegative, and in initially flavivirus-seropositive participants, as measured by PRNT and MN, will be provided at Days 85, 196, 364, 532, and 700 with corresponding 95% CI. The 95% CIs will be calculated based on the t-distribution of the log-transformed values then back transformed to the original scale for presentation. GMT and corresponding 95% CI will be plotted over time. The following descriptive statistics will also be provided at each time point: the number of subjects (n), median, minimum and maximum.
- GMFR of ZIKV-specific nAbs, in all participants, in initially flavivirus-seronegative, and in initially flavivirus-seropositive participants, as measured by PRNT and MN at Days 85, 196, 364, 532, and 700 over pre-vaccination (eg, Visit Day 1 [baseline]) will be tabulated with 95% CI. The 95% CIs will be calculated based on the t-distribution of the difference in the log-transformed values then back

transformed to the original scale for presentation. GMFR and corresponding 95% CI will be plotted over time.

- Proportion of participants with seroconversion in ZIKV-specific nAbs from Day 1 (baseline) to Days 85, 196, 364, 532, and 700, as measured by PRNT and MN will be tabulated with 2-sided 95% Clopper-Pearson CIs.
- Proportion of initially flavivirus-seronegative participants with seroresponse in ZIKV-specific nAb titer at Days 85, 196, 364, 532, and 700, as measured by PRNT and MN will be tabulated with 2-sided 95% Clopper-Pearson CIs.
- Proportion of initially flavivirus-seropositive participants with a ≥2-fold or 4-fold increase in ZIKV-specific nAb titers from Visit Day 1 (baseline) to Days 85, 196, 364, 532, and 700, as measured by PRNT, MN will be tabulated with 2-sided 95% Clopper-Pearson CIs.
- Proportion of all participants, of initially flavivirus-seronegative participants, and of initially flavivirus-seropositive participants with a ZIKV-specific nAb titer equal or greater than a nAb titer defined as a protective level in an animal model, at baseline, and Days 8, 29, 36, 57, 85, 196, 364, 532, and 700, as measured by PRNT and MN will be tabulated.
- Proportion of participants with positive and negative ZIKV-NS1 specific bAbs at Day 29, 57, 85, 196, 364, 532 and 700, as measured by ELISA will be tabulated with 2-sided 95% Clopper-Pearson CIs.
- Proportion of seroconversion in ZIKV-NS1 specific bAbs at Days 29, 57, 85, 196, 364, 532, and 700, as measured by ELISA will be tabulated with 2-sided 95% Clopper-Pearson CIs. The difference of the seroconversion rates between each mRNA-1893 group and placebo group will be provided with 2-sided 95% CIs using the Miettinen-Nurminen method.

Reverse cumulative curves will be provided for ZIKV-specific nAb titers, as measured by PRNT and MN. Similar analyses will be performed for ZIKV-specific bAbs as measured by ligand binding assay.

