5.5. Per-Protocol Sets

The Per-Protocol (PP) Set for Antibody-Mediated Immunogenicity

PP Set for Antibody-Mediated Immunogenicity consist of all FAS participants who

- a) comply with the vaccination schedule,
- b) comply with the timings of immunogenicity blood sampling to have post-vaccination results available for at least one assay component corresponding to the immunogenicity analysis objective (antibody-mediated immunogenicity endpoints), and
- c) have no major protocol deviations that impact immune response during the period corresponding to the immunogenicity analysis objective (antibody-mediated immunogenicity endpoints).

The PP Set for Antibody-Mediated Immunogenicity will serve as the primary population for the analysis of antibody-mediated immunogenicity data in this study. Participants will be included in the vaccination group to which they are randomized.

PP Set for CMI

PP Set for CMI consist of all FAS for Cell-Mediated participants who

- a) comply with the vaccination schedule,
- b) comply with the timings of immunogenicity blood sampling to have post-vaccination results available for at least one assay component corresponding to the immunogenicity analysis objective (CMI endpoints), and

c) have no major protocol deviations that impact immune response during the period corresponding to the immunogenicity analysis objective (CMI endpoints).

The PP Set for CMI will serve as the primary population for the analysis of CMI data in this study. Participants will be included in the vaccination group to which they are randomized.

Participants who did not take blood sample for immunogenicity within [21, 42] days after the second injection date will be excluded from the Per-Protocol Set. Participants who only received 1 dose or who received the second dose outside of the window [21, 42] will be excluded from the Per-Protocol Set.

6. Statistical Analysis

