6.1. General Considerations

The Schedule of Assessments is provided in Appendix E for the vaccination period and the follow-up period, and Appendix F for the extension period.

Continuous variables will be summarized using the following descriptive summary statistics: the number of subjects (n), mean, standard deviation (SD), median, minimum (min), and maximum (max).

Categorical variables will be summarized using counts and percentages.

Baseline value, unless specified otherwise, is defined as the most recent non-missing measurement (scheduled or unscheduled) collected before the first dose of IP. For immunogenicity tests, the baseline is defined as the most recent non-missing measurement (scheduled or unscheduled) collected before or on the date of first dose of IP.

For the summary statistics of all numerical variables unless otherwise specified, the display precision will follow programming standards. Please see Appendix A for variable display standards.

When count data are presented, the percentage will be suppressed when the count is zero in order to draw attention to the non-zero counts. A row denoted "Missing" will be included in count tabulations where specified on the shells to account for dropouts and missing values. The denominator for all percentages will be the number of subjects in that vaccination group within the analysis set of interest, unless otherwise specified.

Study day relative to the first injection will be calculated as below:

a) study day prior to the first injection will be calculated as: date of assessment/event
 date of the first injection;

b) study day on or after the date of the first injection will be calculated as: date of assessment/event – date of the first injection + 1;

Study day relative to the most recent injection will be calculated as below:

- a) study day prior to the first injection will be calculated as: date of assessment/event
 date of the first injection;
- b) study day on or after the date of the first injection but before the second injection (if applicable) will be calculated as: date of assessment/event date of the first injection + 1;
- c) study day on or after the date of the second injection will be calculated as: date of assessment/event – date of the second injection + 1; if study day is on the same day as the second injection, date and time will be compared with the second injection date and time.

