For calculation regarding antibody titers/antibody concentrations, antibody values reported as below LLOQ will be replaced by 0.5 × LLOQ. Values that are greater than the upper limit of quantification (ULOQ) will be converted to the ULOQ. Missing results will not be imputed.

The following stages for safety analyses will be used in this study:

- Up to 28 days after any vaccination: this stage starts at the day of each vaccination
 and continue through the earliest date of (the day of each vaccination and 27
 subsequent days, next vaccination [if applicable]). This analysis period will be used
 as the primary analysis period for safety analyses including unsolicited AE, except
 for solicited AR, unless specified otherwise.
- Up to 28 days after the first vaccination.
- Up to 28 days after the second vaccination.
- Overall stage: this analysis period starts at the first injection on Day 1 and continues through the earliest date of (study completion, discontinuation from the study, or death).

Unscheduled visits: Unscheduled visit measurements will be included in analysis as follows:

- In scheduled visit windows per specified visit windowing rules.
- In the derivation of baseline/last on-treatment measurements.
- In the derivation of maximum/minimum on-treatment values and maximum/minimum change from baseline values for safety analyses.
- In individual subject data listings as appropriate.

Visit windowing rules: The analysis visit windows for protocol-defined visits are provided in Appendix B.

Incomplete/missing data:

- Imputation rules for missing prior/concomitant medications, non-study vaccinations and procedures are provided in Appendix C.
- Imputation rules for missing AE dates are provided in Appendix D.
- For laboratory assessments, if majority of results are indefinite, imputation of these values will be considered. If the laboratory results are reported as below the LLOQ (e.g., <0.1), the numeric values will be imputed by 0.5 × LLOQ in the summary. If the laboratory results are reported as greater than the ULOQ (e.g., >3000), the numeric values will be imputed by ULOQ in the summary.
- Other incomplete/missing data will not be imputed, unless specified otherwise.

Treatment groups:

The following vaccination groups will be used for summary purposes:

- mRNA-1893 vaccine: μg (2-dose)
- mRNA-1893 vaccine: CCI μg (2-dose)
- mRNA-1893 vaccine: μg (single-dose)
- mRNA-1893 vaccine: Total
- Placebo

Summary by flavivirus serostatus:

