6.2. Background Characteristics

6.2.1. Subject Disposition

The number and percentage of subjects in the following categories will be summarized by flavivirus serostatus and vaccination group as defined in Section 6.1 based on Randomized Set:

- Randomized Set
- Solicited Safety Set
- Safety Set
- Full Analysis Set
- Per-Protocol Set

The percentage will be based on subjects in that vaccination group within the Randomization Set (as randomized), except the Solicited Safety Set and Safety Set for which the percentages will be based on the vaccination group in the Safety Set (as treated).

The number of subjects in the following categories will be summarized based on subjects screened:

- Number of subjects screened
- Number and percentage of screen failure subjects and the reason for screen failure

The percentage of subjects who screen failed will be based on the number of subjects screened. The reason for screen failure will be based on the number of subjects who screen failed.

The number and percentage of subjects in each of the following disposition categories will be summarized by baseline flavivirus serostatus and vaccination group based on the Randomized Set, except otherwise specified:

- Randomized by site
- Received each dose of IP
- Prematurely discontinued before receiving the second dose of IP and the reason for discontinuation
- Completed the main study (c.f. Section 4.1, i.e. the period up to Day 196 visit)
- Prematurely discontinued from the main study and the reason for discontinuation
- Continued into the extension period
- Completed the extension period (percentage based on participants who consent to enter the extension period in the Randomized Set)
- Prematurely discontinued from the extention period and the reason for discontinuation (percentage based on participants who consent to enter the extension period in the Randomized Set)

A subject disposition listing will be provided, including informed consent, subjects who completed the study injection schedule, subjects who completed study, subjects who discontinued from study vaccine or who discontinued from participation in the study, with reasons for discontinuation. A separate listing will be provided for screen failure subjects with reasons for screen failure.

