6.4. Immunogenicity Analysis

The analyses of immunogenicity will be based on the PP Set and will be by baseline serostatus group (ie, flavivirus-seropositive, flavivirus-seronegative groups, flavivirus-serostatus missing, and overall) and vaccination group as defined in Section 6.1. Subgroup analysis based on age group (>=18 and < 50 years, >= 50 and <=65 years), gender and region may be performed. If the number of participants in the FAS and PP Set differ (defined as the difference divided by the total number of participants in the PP Set) by more than 10% (for each serostatus group), supportive analyses of antibody-mediated immunogenicity may be conducted using the FAS. The supportive analysis is required if the condition is met at end of study; it is optional for the interim analyses.

The GMT/GMC and geometric mean (GM) level will be calculated using the following formula:

$$10^{\left\{\frac{\sum_{i=1}^{n}\log_{10}(t_{i})}{n}\right\}}$$

where $t_1, t_2, ..., t_n$ are *n* observed immunogenicity titers or levels.

The geometric mean fold-rise (GMFR) measures the changes in immunogenicity titers or levels within subjects. The GMFR will be calculated using the following formula:

$$10^{\left[\sum_{i=1}^{n}\log_{10}\left(\frac{v_{ij}}{v_{ik}}\right)\right]} = 10^{\left[\sum_{i=1}^{n}\log_{10}\left(v_{ij}\right) - \log_{10}\left(v_{ik}\right)\right]}$$

where, for *n* subjects, v_{ij} and v_{ik} are observed immunogenicity titers or levels for subject *i* at time points *j* and *k*, $j \neq k$

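### Antibody percentages default to the whole Per-Protocol arm as denominator, so a participant with no result at a visit counts as a non-responder, mainly at Days 85 to 700

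*SAP*

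**What the plan says.** SAP 6.1 sets a general rule for percentages: "The denominator for all percentages will be the number of subjects in that vaccination group within the analysis set of interest, unless otherwise specified". SAP 6.4 names the set: "The analyses of immunogenicity will be based on the PP Set".

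SAP 6.4.2 to 6.4.4 then list the antibody proportions: seroconversion, seroresponse, 2-fold and 4-fold rise, the share at or above the animal-model protective titer, and NS1 positivity and seroconversion. A typical item is the "Proportion of participants with seroconversion in ZIKV-specific nAbs from Day 1 (baseline) to Days 85, 196, 364, 532, and 700", with Clopper-Pearson intervals. Some items are restricted to one baseline serostatus group. None is restricted to participants with a result at the visit.

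PP membership is defined in SAP 5.5 by dosing and by sampling near Day 57: "Participants who did not take blood sample for immunogenicity within [21, 42] days after the second injection date will be excluded from the Per-Protocol Set". On results, participants need only "to have post-vaccination results available for at least one assay component". No sample at Day 85 or later is required. The Extension Period (Days 364, 532 and 700) needs separate consent at Day 196, and SAP 6.2.1 treats those who decline as having completed the study.

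Two other statements bear on the point. For antibody values, SAP 6.1 says "Missing results will not be imputed". For disposition, SAP 6.2.1 does name a different base: "Completed the extension period (percentage based on participants who consent to enter the extension period in the Randomized Set".

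**The concern.** Read together, these rules keep a PP participant without a sample in the denominator of every later antibody percentage and give that participant no way into the numerator. In effect the missing result is scored as failure, although SAP 6.1 says missing antibody results are left alone. The GMT formula in SAP 6.4 runs over observed titers, and the number with data is reported at each visit. The GMT and the seroconversion rate for one visit would therefore describe different groups of participants.

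At stake is how persistence is read. The protocol gives the duration of the neutralizing response after one or two doses as a reason for the two-year follow-up (Protocol 4.2). A rate that falls because people stop attending would look like a rate that falls because antibody wanes. NS1 is the marker of asymptomatic infection (Protocol 8.3.2), and its seroconversion rate is compared with placebo through Day 700, so missing samples would also lower the apparent infection rate.

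**Working it through.** The plan states no retention, Extension uptake or per-visit number, so it has no figure of its own on this point to reproduce. (SAP Table 2 does reproduce, for example 1 − 0.05^(1/100) = 2.95%, but it concerns adverse-event detection.)

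**Which rule applies**
1. SAP 6.1 sets the default base as arm within analysis set, unless another base is given.
2. SAP 6.4 makes the analysis set the PP Set.
3. SAP 6.4.2 to 6.4.4 give no per-visit base, so step 1 stands.
4. SAP 5.5 fixes PP membership around Day 57, so absence at Day 85 or later does not remove anyone.
5. SAP 6.1 imputes nothing, so an absent participant has no numerator value.

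**Effect on a proportion**

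Let N be the PP participants in the arm and serostatus group, n those with a result at the visit, and x the responders. The default gives x/N = (x/n) × (n/N), which is the rate among those sampled times the share sampled.

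Inputs: N = 100, the planned number per arm and serostatus (SAP 4.3), supposing all are in the PP Set. The 80% rate among those sampled and the share sampled are assumptions.

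| Share sampled | x/n | x/N | Shortfall (points) |
|---|---|---|---|
| 100% | 80/100 = 80% | 80/100 = 80% | 0 |
| 90% | 72/90 = 80% | 72/100 = 72% | 8 |
| 80% | 64/80 = 80% | 64/100 = 64% | 16 |
| 70% | 56/70 = 80% | 56/100 = 56% | 24 |
| 60% | 48/60 = 80% | 48/100 = 48% | 32 |
| 50% | 40/50 = 80% | 40/100 = 40% | 40 |

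At 70% sampled the Clopper-Pearson 95% intervals are 68.7 to 88.6% for 56/70 and 45.7 to 65.9% for 56/100. They do not overlap.

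**NS1**

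SAP 6.4.4 tabulates both positive and negative NS1 proportions. On the default base they add up to n/N, so to 70% rather than 100% when 70% are sampled. For the difference from placebo, if both arms have the same share sampled s, the default gives s × (rate in vaccine arm − rate in placebo). At s = 0.7 the difference shrinks to 0.7 of its value among those sampled. Unequal shares would add a further distortion.

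**Day 57**

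PP entry already requires a sample 21 to 42 days after the second injection. What remains is a sample with no valid PRNT result, since one assay component is enough. Each 1% of such results lowers the reported rate by 1% of itself.

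**If the addendum sets the base**

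SAP 6.6 reports data after Month 8 in an addendum for Extension enrollees. If their number replaced N, decliners would drop out and only missed visits and later dropouts would count as failures. Assuming 80 of 100 enrolled and 70 sampled, 56/80 = 70%: a shortfall of 10 points rather than 24. Days 85 and 196 would be unchanged.

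**The case against.** The best reply is that the plan is unclear rather than wrong, and that its authors probably meant observed cases.

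- **Endpoint-specific sets.** SAP 5.4 ties the FAS to a post-vaccination assessment for the endpoint, and PP is drawn from the FAS. The set could therefore vary by endpoint, which would take a participant with MN but no PRNT out of the PRNT analysis. But a result at another visit can satisfy that wording, and the disposition table in SAP 6.2.1 counts one FAS and one PP Set, not one per visit.
- **The addendum's scope.** It may well exclude decliners from the later tables. It defines the scope of a report, however, not a denominator, and missed visits would still count as failures. It limits the size and leaves the direction unchanged.
- **No imputation.** The rule on missing antibody results is the more specific one and points to an observed-case intention. It does not say who leaves the denominator. The table shells might, but they are not among the documents.
- **Low consequence.** This stands. The Day 85 to 700 endpoints are exploratory, no hypothesis is tested, Phase 3 progression rests on the Day 57 interim analysis, and the n shown with each GMT would let a careful reader recompute the rate.

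A reader might also infer that differing Extension uptake will create false differences between regimens. The arithmetic allows it: 90% among those sampled in two arms, with 70% and 60% sampled, would show as 63% and 54%. But nothing in the documents suggests unequal attendance, since arms are randomized and participants and sites stay blinded. At Days 85 to 700 a formal between-arm difference is planned for NS1 only, not for neutralizing-antibody seroconversion.

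**Conclusion.** The point holds. Taken literally, the SAP scores a PP participant with no result at a visit as a non-responder, against its own statement on missing antibody results and out of step with the GMT and GMFR beside it. The direction is certain once any result is missing and any sampled participant responds. The size is not known. The 24-point shortfall rests on an assumed 70% sampled and 80% responding, and it is smaller at Days 364 to 700 if the addendum limits the base to Extension enrollees.

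The effect falls mainly on the exploratory Day 85 to 700 proportions and on NS1 seroconversion with its difference from placebo.

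Two stronger readings are tempting and not supported. One is that the primary Day 57 seroconversion rate is materially lowered: PP entry requires a sample in the window, and no frequency of invalid PRNT results is given. The other is that reported persistence must equal persistence times Extension uptake: that needs decliners to stay in the base, which the addendum's scope leaves open. Nor is the rate among those sampled necessarily the true rate for the arm. It is so only if absence is unrelated to antibody level.

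**What to change.** Add one statement to SAP 6.4. Each antibody proportion, and any difference between arms, uses participants in the analysis set with a non-missing result for that assay at that visit, and a non-missing baseline where the endpoint needs one. Show it as n/N1 with the number missing. Apply it to seroconversion, seroresponse, fold rise, the protective-titer share and NS1. For the Extension visits, also say whether the analysis set is limited to enrollees, so that the number missing has a defined base.

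A version counting missing results as failures can be kept as a labelled sensitivity analysis.

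The cost is that statement and changes to table headers. The drawback is that the rate then describes only those sampled, which is why the number missing needs to appear beside it.

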6.4.5. Analysis of CMI Endpoints

The CMI assessments will be performed with the additional blood samples collected for peripheral blood mononuclear cells (PBMC) isolation from the CMI subset participants, the analysis details will be provided in a separate document.

6.4.6. Sensitivity Analysis

Sensitivity analysis for selected immunogenicity endpoints may be performed with the same methods described above by baseline flavivirus status determined by serology testing.

6.5. Analysis of occurrence of Flavivirus Infection

Analyses of flavivirus infection will be performed using the FAS. The number and percentage of subjects with at least one positive flavivirus result (Dengue PCR, ZIKV PCR) post-baseline and occurring at any time during the study duration will be provided by baseline flavivirus serostatus and treatment arm. Subjects with at least one positive flavivirus result at post-baseline will be presented in a listing.

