8.3.2. Efficacy Assessments

Blood samples for detection of asymptomatic flavivirus infection will be collected as described in Table 1 and Table 2. Asymptomatic flavivirus infections will be assessed through quantification of nonstructural protein 1-specific bAbs, as measured by enzyme-linked immunosorbent assay (ELISA).

In case of signs or symptoms suggesting a flavivirus infection (mostly dengue and Zika in the areas where the study will be performed), an additional blood sample will be collected to confirm the diagnosis via specific serology (IgM antibody capture ELISA and virus neutralization assay) and RT-PCR.

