2.3. Exploratory Objectives

The exploratory objectives are the following:

- To evaluate the duration of the humoral immune response of 2 dose levels of mRNA-1893 at Days 85, 196, 364, 532, and 700, as measured by ZIKV-specific neutralization assay (PRNT and MN), in comparison to a placebo control, in flavivirus-seronegative participants at baseline and in flavivirus-seropositive participants at baseline.
- To evaluate the humoral immunogenicity of 2 dose levels of mRNA-1893, as measured by ligand binding assay, in comparison to a placebo control, in flavivirus-seronegative participants at baseline and in flavivirus-seropositive participants at baseline.
- To evaluate the ZIKV-specific cellular immune response of 2 dose levels of mRNA-1893 in comparison to a placebo control in flavivirus-seronegative participants at baseline and flavivirus-seropositive participants at baseline (cell-mediated immunity [CMI] subset of participants).
- To assess the occurrence of flavivirus infections throughout the entire course of participation in the study in comparison to a placebo control.

3. Study Endpoints

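### SAP 6.5 counts flavivirus infection by PCR only, while NS1 seroconversion sits in a separate, narrower table and acute-case serology is not analysed at all

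*SAP*

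**What the plan says.** The exploratory objective in SAP 2.3, repeated from Protocol Table 5, is "To assess the occurrence of flavivirus infections throughout the entire course of participation in the study in comparison to a placebo control".

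SAP 6.5 states that "Analyses of flavivirus infection will be performed using the FAS". It counts participants with "at least one positive flavivirus result (Dengue PCR, ZIKV PCR) post-baseline" by baseline serostatus and arm, and the accompanying listing uses a positive result in the same sense.

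Protocol 8.3.2 is broader. For suspected illness, an additional blood sample is taken to "confirm the diagnosis via specific serology (IgM antibody capture ELISA and virus neutralization assay) and RT-PCR". For silent infection, "Asymptomatic flavivirus infections will be assessed through quantification of nonstructural protein 1-specific bAbs".

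NS1 is handled elsewhere in the SAP. Section 6.4.4 tabulates "Proportion of participants with positive and negative ZIKV-NS1 specific bAbs" and "Proportion of seroconversion in ZIKV-NS1 specific bAbs" at Days 29 to 700 with Clopper-Pearson intervals. For seroconversion it adds Miettinen-Nurminen differences between each vaccine group and placebo.

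**The concern.** The objective speaks of infections over the whole of participation, but the table that carries that name can show only PCR-confirmed symptomatic illness. A reader who takes the 6.5 row as the infection count for an arm will read it too low. The extension to Day 700 is justified in Protocol 2.2 and 4.2 partly by the chance to observe flavivirus infections, so this is one of the results the long follow-up is meant to deliver. A suspected case with positive serology and negative PCR would be missing from both the 6.5 table and its listing, although the protocol collects the result.

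**Working it through.** The plan gives no figure for infections, so the check is mainly a comparison of definitions.

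| | SAP 6.5 | SAP 6.4.4 (NS1) | Acute-case IgM and neutralization |
|---|---|---|---|
| Sample | Unscheduled, triggered by symptoms | Days 29, 57, 85, 196, 364, 532, 700 | Unscheduled, triggered by symptoms |
| Criterion | Dengue or Zika PCR positive | Zika NS1 negative at baseline, positive later | None stated |
| Analysis set | FAS | PP Set (SAP 6.4) | None |
| By arm | Number and percentage | Proportions, and differences from placebo | None |

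1. **Where PCR results come from.** In Protocol Tables 1 and 2 the sample for symptomatic infection appears only in the unscheduled column. Tables 9 and 10 budget dengue and Zika PCR blood only for participants with suggestive signs or symptoms. An asymptomatic infection therefore cannot enter 6.5.

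2. **Acute-case serology.** The footnotes to SAP Appendices E and F repeat that suspected cases are confirmed by serology and RT-PCR. Neither 6.4 nor 6.5 tabulates the serology.

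3. **Why the NS1 table cannot simply be added to the PCR count.**
   - SAP 5.5 removes from the PP Set participants with one dose, with the second dose outside the 21 to 42 day window, or without a blood sample 21 to 42 days after it. An infection in such a participant is outside 6.4.4.
   - SAP 3.3 defines NS1 seroconversion as negative to positive only. The notes to Protocol Table 5 also accept a rise of at least 4-fold. Under the SAP rule, a participant who is NS1-positive at baseline can never count. SAP section 7 records no change from the protocol.
   - The SAP names Zika NS1 only, so asymptomatic dengue has no named analysis.
   - The two sections are not cross-referenced, and no rule avoids counting a participant twice.

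4. **Direction.** PCR positives are a subset of participants positive by PCR or NS1, so N(PCR) ≤ N(PCR or NS1). The inequality is strict as soon as one NS1 seroconverter lacks a positive PCR.

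5. **Size, as an illustration only.** Let s be the share of infections that are symptomatic and sampled, and q the share of those that are PCR-positive. Section 6.5 then sees s × q of all infections. Neither input is in the documents. With assumed ranges s = 0.2 to 0.8 and q = 0.5 to 0.9:
   - low end: 0.2 × 0.5 = 10%
   - high end: 0.8 × 0.9 = 72%

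   The rate giving a 95% chance of at least one event among 200 is 1 − 0.05^(1/200) = 1.49%, which matches the adverse-event figure in Protocol Table 11 and SAP Table 2. For at least one case counted in 6.5 in an arm of 200, the true infection rate would have to be 1.487% / 0.72 = 2.1% to 1.487% / 0.10 = 14.9%. The width of that range shows how little can be said about size.

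**The case against.** The strongest reply is that NS1 seroconversion is one of the two endpoints the protocol lists for this objective, and SAP 6.4.4 analyses it by arm with differences from placebo. PCR is not a listed endpoint, so 6.5 adds to the NS1 analysis rather than replacing it. This stands against one tempting reading, that asymptomatic infections go unanalysed: they do not, at least for Zika. It does not remove the gap, because the two results use different sets, cannot be combined from the tables, and the NS1 rule is narrower than the protocol's.

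Three further replies also stand.

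- A reader might infer that every serology-positive case is an infection wrongly counted as none. Protocol 8.3.2 calls for "specific serology (IgM antibody capture ELISA and virus neutralization assay) and RT-PCR" but does not say whether either test alone suffices, and it gives no serological threshold. If both were required, a PCR-only rule could even be too generous for symptomatic cases.
- Adding serology without a rule could do harm. Protocol 2.2 says the vaccine is directed at the Zika prME proteins, and it is meant to raise Zika neutralizing antibody. Counting neutralization as proof of infection could misclassify febrile vaccinees and bias the comparison with placebo. NS1 is not in the stated antigen. The SAP does not give this as its reason for using PCR alone.
- A reader might infer that monitoring for enhanced disease depends on this table. Protocol 2.3.2 assigns that to blinded review by the Oversight Safety Team and unblinded DSMB review of adverse events.

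**Conclusion.** The point holds for the 6.5 table. It counts PCR positives only, these can arise only from the symptomatic sample, and it therefore understates infection occurrence relative to a count that includes NS1. The acute-case IgM and neutralization results have no analysis in the SAP.

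The size cannot be derived. The 10% to 72% range rests wholly on assumed inputs and describes what 6.5 sees, not what the SAP as a whole loses, since 6.4.4 reports part of the remainder. The direction rests on treating NS1 seroconversion as evidence of infection, as Protocol 8.3.2 does.

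The objective is exploratory and the study tests no hypotheses, so no primary or secondary result is affected. The change is worth making because it is cheap and the data are already planned.

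**What to change.** In SAP 6.5, on the FAS, by arm and baseline serostatus, report:

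- (a) PCR-confirmed symptomatic infection.
- (b) NS1 seroconversion, using the protocol definition with its 4-fold-rise route. If the negative-to-positive rule is kept, record the departure in SAP section 7.
- (c) Any infection, meaning (a) or (b), with each participant counted once. An NS1 seroconverter with a PCR-confirmed symptomatic episode is classed as symptomatic. Show PCR-only as a sub-row.

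List the IgM and neutralization results of suspected cases, and report serology-only suspected cases in a separate row outside (c). State that Zika neutralization alone does not define a case. Cross-refer to 6.4.4, and say plainly that the NS1 component covers Zika only if that remains so.

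The cost is SAP text and a few derived variables; no new sampling is needed. The downside is that NS1 and serology are less virus-specific than PCR, which is why the PCR-only row should stay visible.
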